Adolescent anorexia nervosa is a severe eating disorder related to long-lasting morbidity and premature mortality (1, 2), and recent reports from hospitals suggests the prevalence in Norway may be increasing (3). The manualised family therapy “Family Based Treatment” (FBT) is currently the treatment approach for adolescent anorexia nervosa with the largest evidence base (4). FBT is recommended as a first line treatment in multiple service contexts (5, 6).

While there has been conducted several randomised controlled trials of FBT in academic settings (7), there are few large studies examining outcomes when FBT is implemented in clinical practice. A

systematic review published in 2015 found five such dissemination studies. Of these, three were conducted in academic clinical settings with the number of patients ranging from 11 to 20, and two were retrospective studies reporting changes in service use patterns after implementation of FBT in a regular mental health service (8). Two later studies have compared the outcomes achieved in clinical trials of FBT to those of FBT provided in regular clinical care, finding these to be comparable (9, 10), but these have both been conducted in highly specialised clinical contexts. More studies with higher power are needed to confirm the effectiveness of FBT when disseminated to regular healthcare contexts.

At the Child and Adolescent Mental Health Service (CAMHS) unit Nedre Romerike BUP, adolescent anorexia nervosa has consistently been treated with family therapy for about 20 years. In 2018 the unit implemented FBT, making several changes to the form of family therapy provided. As part of treatment monitoring, patients are weighed regularly, and weight data are recorded in patient health records.

Restrictive eating and corresponding weight loss are core features of anorexia nervosa, besides distorted views of the body and rigid preoccupation with losing weight and avoiding weight gain. Normalisation of eating behaviour and weight status is hence the primary treatment goal, making the patient health records in this case contain relevant outcome data.

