The long-term course of anorexia nervosa is heterogeneous, and in some patients the disorder shows a protracted course, with long term morbidity and functional impairment, as well as increased mortality (11). There are few longitudinal studies of treatment outcomes with long follow-up periods (12). As Norway has a general system of personal identification numbers, following up patients across multiple public registries is a viable way to assess long term outcomes without the patients needing to participate in reporting.

AIMS

The primary aim is to assess the short and long-term effectiveness of FBT compared with non-manualised family therapy. This is operationalised as testing whether the adoption of FBT has led to patients achieving normalisation of weight faster than with the previously delivered family therapy, and whether it will lead to less treatment provided for eating disorders in adulthood. Secondary aims are to assess whether adoption of FBT have resulted in reduced time to discharge, changed the heterogeneity of weight gain across patients, whether there have been changes in the rates of adverse events and readmissions, and to assess whether the implementation of FBT has led to changes in long-term functional status and rate of mortality.

DESIGN AND METHODS

Participants and recruitment

This is a two-group retrospective exploratory cohort study with prospective longitudinal follow-up in public registries. Eligible participants are all patients initiating treatment during the years 2015-2020 with the eating disorder team at Nedre Romerike BUP with a primary ICD-10 diagnosis of F50.0 Anorexia nervosa or F50.1 Atypical anorexia nervosa. Patients will be excluded if they were treated during the years 2018-2020 and FBT was never initiated. It is estimated that the final sample size will be approximately 200.

Eligible participants will be identified through review of patient health records. Participants will be contacted by letter with information about the study, including a link to an online video explaining more about the study. Study personnel will make a follow-up telephone call approximately a week later to allow the eligible participant to ask any questions they may have before deciding on participation in the study. Participants who are interested in participating will be directed to a website

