where they can sign an electronic consent form and complete a short survey about their experience of treatment. The consent form and treatment experience survey will be implemented in “Tjenester for Sensitive Data”, which has appropriate security and allows for verified electronic signatures.

Participants will be contacted after they have reached age 16, and thus are able to give informed consent. They will be encouraged to discuss participation with their parents or other legal guardians.

Endpoints and data collection

Primary endpoint for the retrospective study is weight restoration, defined by patients having a weight measurement placing them at or above 95% of expected body weight (50. percentile) for age given Norwegian population norms, following established definitions of weight restoration (10).

Secondary endpoints are discharge from treatment and readmission to treatment (the latter is assumed to be right-censored).

Adverse events will be defined as debut of suicidal ideation, attempted suicide, debut of self-harming behaviour, severe self-harm where medical attention is indicated, hospitalisation for low weight or medical complications from low weight, admission to inpatient treatment for anorexia nervosa, involuntary gastric tube feeding, parental separation, and initiation of contact with child protective services.

Participant experiences and satisfaction with services will be assessed using the Generic Short Patient Experiences Questionnaire (GS-PEQ) (13).

The primary endpoint for the prospective study is continued morbidity, defined as being currently in treatment in specialist health care for any eating disorder. Secondary endpoints are mortality, level of education and employment status.

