We will evaluate whether adoption of FBT has led to faster weight normalisation by fitting a parametric survival model to the number of days until weight restoration is achieved. We will also fit models with gender, age, baseline weight, comorbid disorders and family structure as covariates, and further investigate whether any of these act as moderators of FBT compared with previous treatment. Similar parametric survival models will also be used for modelling differences in time to discharge and readmission. Differences in the rate of adverse events will be modelled using Poisson regression.

We will also evaluate differences between the cohorts in treatment course by fitting multilevel spline models to weight data with knots for every 4 weeks in treatment. Weight measurements will be nested within patients, and patients nested within cohorts. Spline models will allow for modelling non-linear weight change over the course of treatment, and the multilevel structure at the patient level will allow us to evaluate changes in heterogeneity of treatment response pre and post adoption of FBT, as well as visualise trends and heterogeneity of weight change across the course of treatment.

Analysis of prospective data will use parametric survival models or logistic or ordinal regression models, depending on the level of time specificity available in the data.

We have conducted simulations to investigate statistical power, assessing the type S (sign) and type M (magnitude) error rates, given inference based on the posterior median. We made the assumption of achieving at least a sample size of 150 patients and that implementation of FBT has led to a 10% increase in the probability of an event (i. e. weight restoration or discharge). With 1000 simulations, we estimated a type S error of 0.00 and an M error of 0.89, suggesting a very low risk of estimating the sign of the effect incorrectly and a small risk of underestimating the effect size. We conclude that the study will be adequately powered to achieve its primary aim.

The analysis will employ weakly informative prior distributions, using previous studies and other external knowledge (for instance about the biological limits of weight gain per day) to construct priors that rule out impossible areas of the parameter space (17).

ETHICAL CONSIDERATIONS

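### With no family, follow-up end, censoring rule or horizon fixed, an exponential or Weibull fit to time to weight restoration can show a spurious FBT effect if treatment length differs and some patients never restore

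*Combined protocol and SAP*

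**What the plan says.** - **Model.** The Analysis plan answers the primary retrospective question by "fitting a parametric survival model to the number of days until weight restoration is achieved". It gives no family, no baseline shape, no cure component and no check of fit.
- **Event.** Under Endpoints and data collection the event is "weight restoration, defined by patients having a weight measurement placing them at or above 95% of expected body weight". No time limit is attached.
- **Censoring.** Right-censoring appears once, for "readmission to treatment (the latter is assumed to be right-censored". Nothing says how a patient who never reaches the threshold enters the primary model, or when that patient's follow-up ends.
- **Source of weights.** The Background states: "As part of treatment monitoring, patients are weighed regularly, and weight data are recorded in patient health records". Endpoints and data collection adds a manual search of records for further weights.
- **Treatment length.** A secondary aim is to assess "whether adoption of FBT have resulted in reduced time to discharge".
- **Course of illness.** The Background notes that "in some patients the disorder shows a protracted course".

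**The concern.** A standard exponential or Weibull model has no plateau: given enough time, everyone is predicted to restore. If a share of patients never does, the later follow-up consists increasingly of those patients, and their event-free time pulls the fitted hazard down. The cohort observed longer holds more of that time and so gets the lower hazard. This can happen when the restoration process is identical in both cohorts and discharge is unrelated to outcome, so it is a misfit of model shape and separate from informative drop-out.

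At stake is the primary retrospective conclusion. A finding of faster restoration could partly reflect shorter treatment, which the plan treats as a separate, secondary question.

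**Working it through.** **The plan's own figure.** The power simulation reports a type S error of 0.00 and an M error of 0.89 for 150 patients and a 10% increase in event probability. It cannot be reproduced: baseline rate, time unit, family, prior and the scale of the 10% are not given. If the 10% is read as a hazard ratio of 1.10 and all 150 patients have events, SE = 2/√150 = 0.163, ln 1.10 = 0.095 and z = 0.58, so P(wrong sign) is about 0.28. That is only one reading, but it gives a yardstick for the distortions below.

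**Inputs.** The model, the event and the silence on censoring come from the documents. Restoration rates and treatment lengths are not given and are assumed. Maximum likelihood stands in for the Bayesian fit because no prior values are stated. A false finding means a 95% interval wholly on the FBT side, nominally 2.5%; the plan sets no such rule.

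**Mechanism by hand (exponential).** Fitted hazard = events / person-time. Per 100 patients, let 60 restore, with Weibull times of shape 1.5 and median 150 days. The scale is 150/(ln 2)^(1/1.5) = 191.5 days, and the mean is 191.5 × Γ(1.667) ≈ 173 days. The other 40 contribute on average 500 days before FBT and 300 days with FBT.
- Before FBT: 60/(60×173 + 40×500) = 60/30,380 = 0.00197 per day.
- With FBT: 60/(60×173 + 40×300) = 60/22,380 = 0.00268 per day.

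The ratio is 1.36 with identical restoration. This overstates the effect, because earlier discharge also cuts off some restorations. Allowing for that by simulation gives 1.21.

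**Simulation A, no FBT effect.** Same restoration times. Unrestored patients leave at 300-700 days before FBT and 150-450 days with FBT, so mean length falls from 500 to 300 days (1 − 300/500 = 40%).
- Large-sample Weibull hazard ratio with 0%, 20% and 40% never restoring: 0.99, 1.13, 1.21. Cox: 0.99, 0.98, 1.01.
- 75 per arm, 40% never restoring: 15% of Weibull intervals falsely favour FBT (12-17% across independent repeats), against 2.2% for Cox; 80% of Weibull point estimates favour FBT.
- 75 per arm, 20% never restoring: about 10% for Weibull, about 2% for Cox.
- 40% never restoring, treatment 20% shorter: Weibull about 12%, log-normal about 4%.
- 40% never restoring, treatment 10% shorter: Weibull hazard ratio 1.05 with 4% false-favourable; log-normal time ratio 0.98 with 3%.

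**Simulation B, no FBT effect.** Independent set-up: N = 200 split 1:1, median restoration 5 months, gamma discharge times with CV 50%, 400 replicates. Monte Carlo SE is about 1 point near 2.5% and 2 points near 15%. The entries are false-favourable rates.

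| Able to restore | Mean months, before / with FBT | Exponential | Weibull | Log-normal |
|---|---|---|---|---|
| 60% | 18 / 15 | 9.2% | 7.5% | 2.8% |
| 60% | 18 / 12 | 18.8% | 14.2% | 4.0% |
| 60% | 18 / 9 | 25.5% | 21.0% | 5.0% |
| 80% | 18 / 12 | 10.2% | 13.0% | 3.5% |

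- The large-sample Weibull hazard ratio for 60%, 18 / 12 is 1.16.
- With lengths reversed (12 / 18, 60% able to restore), the Weibull is falsely against FBT in 12.8% of runs.
- With equal lengths, the ratio is about 1.0 and no rate exceeds 4.5% in either direction.
- If all patients can restore, the correctly specified Weibull has a time ratio of 0.98, which is no material bias.

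**Remedies in the 60%, 18 / 12 case.** False-favourable rates are 1.5% for Cox and 1.8% for a Weibull cut at a common 6 months. A mixture-cure model gives 4.3% for speed and 0.7% for the share restored. For a Weibull, a common 12-month cut alone leaves a hazard ratio of 1.02 here and 1.06 in simulation A with 40% never restoring.

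**If observation does not stop at discharge.** With never-restorers followed to a calendar cut-off (assumed 60-96 months for the earlier cohort, 24-60 for FBT), false-favourable rates are 79% for exponential, 27% for Weibull and 9% for log-normal.

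**The case against.** The strongest reply is that the plan does not commit to the models that fail. It says parametric without naming a family. Log-normal is only slightly affected (false-favourable about 3-5% under unequal discharge), and log-logistic gives about 5% in simulation A. A mixture-cure model is itself parametric and would comply with the plan. This stands: the defect is an open specification, and parametric modelling as such is not shown to be wrong. But a default Weibull or exponential fit complies equally, and nothing steers the analyst away from it.

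Second, the conditions are not documented. A reader might infer that the sponsor expects shorter treatment. The Aims only ask whether discharge comes sooner, and the assumed rise in discharge probability is an input to the power simulation. The remark on protracted illness concerns long-term course; it does not say what share never once reaches the threshold. Follow-up ending at discharge is also inferred, since the manual record search has no stated stopping point. All three limits stand, and a length difference of about 10% would leave little bias.

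Third, a common horizon removes most of the bias without a change of family. That is largely true, although a 12-month cut alone leaves some. The planned multilevel spline trajectories offer a partial cross-check on faster weight gain, but they do not correct the survival estimate.

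**Conclusion.** The concern holds conditionally, and the specification should be tightened before analysis. With 20-40% never restoring and treatment 20-40% shorter under FBT, both assumed, a Weibull fit gives a null hazard ratio of about 1.07-1.2 and about 8-17% false-favourable intervals instead of 2.5%. If the planned 10% increase means a hazard ratio of 1.10, the distortion is of the same order as the effect sought. That matters for inference based on the posterior median and its sign.

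A reader might go further and conclude that the planned analysis will produce a false FBT effect. The documents do not support that. The bias needs both a real difference in observation length and a share of never-restorers, neither of which is quantified. Its size depends on the unnamed family, and its direction on which cohort is observed longer. Even where it occurs, it raises the chance of a false finding without making one certain.

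**What to change.** Before analysis, amend the Analysis plan as follows.

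1. State when follow-up for restoration ends and how patients who have not restored are censored.
2. Follow both cohorts to one common horizon from treatment start, for example 12 months.
3. As the lead model in brms, use a flexible baseline hazard shared by the cohorts (M-spline, Cox-type) or a mixture-cure model. Report the restoration probability at the horizon and the difference in restricted mean days to restoration.
4. Check the fit against Kaplan-Meier curves by cohort, and keep a simple parametric fit, with its family named, as a sensitivity analysis.
5. Add an analysis treating discharge before restoration as a competing event. A flexible baseline does not remove bias from informative discharge: when never-restorers were discharged in half the time in the FBT cohort only, the null Cox hazard ratio was 1.40 (Weibull 1.78).

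The cost is plan wording and a different model specification in the same package, with no new data. Intervals will be slightly wider, and the lead analysis will not use events after the horizon.

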Data for the retrospective part of the study will be extracted from electronic patient health records. Weight data will be extracted directly from the electronic patient health record system (DIPS). One researcher will further go manually through all records of included patients and extract dates of treatment start, adverse events, discharge and any readmission, as well as checking the record for any weight measurements recorded but not entered into the weight database. As covariates we will also extract age, sex, gender, family structure, extent of care benefits received during treatment (pleiepenging), and comorbid disorders (ICD-10 diagnoses). Another researcher will independently extract data from a random 10% subsample for control and reliability assessment of coding.

Each participant will be assigned a random case identity number, which will be used for identification in all dataset files when data is analysed. Participant national identity numbers will be stored along with the corresponding case identity number in a separate file, the identity key file. Access to the identity key file will be restricted to the project manager and researchers performing data extraction. It will also be delivered to the agencies maintaining the relevant public registries.

When extracted, data will be entered directly into a REDCap database maintained by Akershus university hospital. Access will be restricted to researchers in the project group. Data will be stored and analysed de-identified.

Data for the prospective part of the study will be acquired from the following public registries: Norwegian Patient Registry, Norwegian Cause of Death Registry, and the databases “Attachment to employment, education and welfare benefits” and “Educational attainment of the population” collated by Statistics Norway. Data will be acquired from these databases in three waves; five, ten and twenty years after the last participant initiated treatment. All registry data will be acquired, stored and analysed de-identified.

Analysis plan

Statistical analysis will be conducted in a Bayesian framework using the Stan platform through the R (14) package brms (15).

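### The index diagnosis (F50.0 or F50.1) is in none of the lists of covariates, adjusters or moderators, so a difference in diagnosis mix between the calendar cohorts could be partly read as an FBT effect

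*Combined protocol and SAP*

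**What the plan says.** Under Participants and recruitment, eligibility covers "all patients initiating treatment during the years 2015-2020" with the unit's eating disorder team who have "a primary ICD-10 diagnosis of F50.0 Anorexia nervosa or F50.1 Atypical anorexia nervosa". The Background section dates the change of treatment: "In 2018 the unit implemented FBT, making several changes to the form of family therapy provided". The comparison is therefore one calendar period against another. One filter applies to the later period only: "Patients will be excluded if they were treated during the years 2018-2020 and FBT was never initiated".

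Under Endpoints and data collection, the extraction list begins "As covariates we will also extract age, sex, gender, family structure" and goes on to care benefits and comorbid disorders. Comorbid disorders are its only ICD-10 item.

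Under Analysis plan, the time-to-weight-restoration model is first stated without covariates. The plan then adds: "We will also fit models with gender, age, baseline weight, comorbid disorders and family structure as covariates". Moderators are to be sought among these same variables. Discharge and readmission get similar survival models. No covariates are named for the Poisson model of adverse events or for the registry models.

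No section stratifies or restricts by F50.0 versus F50.1, plans a sensitivity analysis on it, or compares the diagnosis mix between cohorts.

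**The concern.** The index diagnosis is a baseline characteristic that has to be read for every patient to establish eligibility. A comorbid disorder is by definition not the primary diagnosis, so the comorbidity covariate does not cover it.

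In a randomised comparison, leaving it out would cost little. Here nothing balances the cohorts. The mix could differ through changes in referral over 2015-2020. It could also differ through the one-sided exclusion, if starting FBT depended on diagnosis. The primary endpoint is a weight threshold (95% of expected body weight), and the two diagnostic groups need not start equally far from it.

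Two things are at stake. A difference in mix could add to or subtract from the estimated FBT effect. And without diagnosis as an analysis variable, a reader could not tell whether the mix changed, or whether the result holds for F50.0, the condition named in the title.

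**Working it through.** **The plan's own figures.** The documents give no diagnosis shares and no diagnosis-specific rates, so there is nothing to reproduce on this point. The only yardstick is the planning effect under Analysis plan, a 10% increase in event probability. The reported type S and type M errors do not bear on this point.

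**Assumed inputs.** F50.1 share a = 0.20 in the earlier cohort and b = 0.40 in the FBT cohort; rate of weight restoration in F50.1 relative to F50.0, r = 1.5 or 2; true FBT hazard ratio 1.00.

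**Crude model, by hand.** With exponential times, the crude hazard ratio lies between two limits.

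- Very short follow-up, ratio of mean rates: (1 − b + b·r) / (1 − a + a·r). For r = 1.5: 1.20/1.10 = 1.091. For r = 2: 1.40/1.20 = 1.167.
- Complete follow-up, ratio of mean times: (1 − a + a/r) / (1 − b + b/r). For r = 1.5: 0.933/0.867 = 1.077. For r = 2: 0.90/0.80 = 1.125.

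**Adjusted models, by simulation.** An exponential survival model was fitted to 400,000 simulated patients. Half of the diagnosis effect was assumed to act through baseline weight, with the diagnoses 1 to 1.5 SD apart in weight. The figures repeat to within 0.01.

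| r | Crude | Baseline weight added | Weight and diagnosis added |
|---|---|---|---|
| 1.5 | 1.08 | 1.03-1.04 | 1.00 |
| 2 | 1.13-1.14 | 1.05-1.06 | 1.00 |

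**How the result depends on the inputs.**

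- No change in mix: 1.00 in every model.
- Shift from 20% to 30% only: crude about 1.04 (r = 1.5) and 1.06-1.07 (r = 2); with baseline weight about 1.01-1.02 and 1.03.
- Share falling from 40% to 20%: the reciprocal of the crude figures, 1/1.08 = 0.93 and 1/1.13 = 0.88, so the bias runs against FBT.
- Baseline weight unrelated to diagnosis: adjusting for weight removes nothing (1.08 and 1.14 remain).

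**Against the planning effect.** The plan does not say whether 10% is relative or absolute. Under proportional hazards, HR = ln(1 − p₂)/ln(1 − p₁), where p₁ is the control probability. Take p₁ from 0.3 to 0.8, again an assumption.

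- Relative 10%: ln(0.67)/ln(0.70) = 1.12, up to ln(0.12)/ln(0.20) = 1.32.
- Absolute 10 points: about 1.31 (p₁ = 0.6, ln(0.30)/ln(0.40)) to 1.43 (p₁ = 0.3, ln(0.60)/ln(0.70)).

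On the log scale, the weight-adjusted bias is between ln(1.03)/ln(1.43) = 0.08 and ln(1.06)/ln(1.12) = 0.51 of the planning effect. The crude bias is between ln(1.08)/ln(1.43) = 0.22 and ln(1.13)/ln(1.12) = 1.08.

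**The case against.** The strongest reply has four parts.

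- *Nothing shows that the mix changed.* This stands. A reader might infer that the comparison is biased; the documents support only that it could be, and that as planned no one would be able to see it.
- *Baseline weight is already an adjuster, and it is the covariate closest to a weight-threshold endpoint.* This stands in part. Under the assumptions above it removes half or more of the bias. It does nothing for the model without covariates.
- *The diagnosis is read at eligibility, and the covariate list says what is also extracted, so the diagnosis may well be on file.* Fair. A reader might infer that it goes unrecorded; the text shows only that it is not among the listed covariates, adjusters or moderators.
- *Adjusting for a label can itself create bias.* If the patients stayed the same but the team's use of F50.1 drifted after 2018, the unadjusted comparison is right and the adjusted one is wrong. Suppose the F50.1 label moves from 20% to 40% through a change of threshold alone, with a label rate ratio of about 1.5-2.1 and weight correlated 0.7 with severity. A simulation with no FBT effect then gives 0.99-1.01 crude or weight-adjusted, about 0.93 to 0.89 with diagnosis added, and about 0.92 to 0.87 in F50.0 alone. This stands. It is a reason to show both versions and not to force diagnosis into every model. It is not a reason to leave diagnosis out.

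The absence of stated covariates for adverse events and registry outcomes is a general gap, not one specific to diagnosis. The models for readmission and discharge are described as similar to the main one, so they can be read as carrying its covariates.

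**Conclusion.** The point holds as a conditional weakness. A baseline characteristic that defines eligibility is missing from the lists of covariates, adjusters and moderators in a non-randomised comparison of calendar periods, with a selection filter on one side only. A difference in the F50.0/F50.1 mix could therefore be partly read as an FBT effect. Size and direction cannot be known from the documents. For an assumed 20% to 40% shift and a rate ratio of 1.5-2, the spurious hazard ratio is about 1.08-1.13 crude and 1.03-1.06 after baseline-weight adjustment. The adjusted figure also assumes that half of the diagnosis effect runs through weight.

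A reader might infer that the bias would match the planned effect. That is supported only for the model without covariates, and only at the unfavourable end: relative reading, low event probability, r = 2. For the weight-adjusted model under these inputs, the bias is at most about half of the planning effect and often much less.

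**What to change.** Under Endpoints and data collection, add primary diagnosis at treatment start (F50.0 or F50.1) to the extracted variables, and plan a table of its distribution by cohort.

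Under Analysis plan:

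- Add it to the covariates of the adjusted weight-restoration model and of the similar discharge and readmission models.
- Report each adjusted result with and without it.
- Report the weight-restoration contrast in F50.0 alone as a sensitivity analysis.
- Label any moderator estimate by diagnosis as exploratory.

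The cost is one field that is already read for eligibility and one binary term per adjusted model. The moderator estimate will be imprecise. With two equal cohorts of 75, F50.1 shares of 20% and 40% and, at best, an event in every patient, the standard error of the log ratio of hazard ratios is √(1/15 + 1/60 + 1/30 + 1/45) = 0.37. The 95% limits then lie a factor of about 2.1 either side. With 200 patients the factor is about 1.9 (√(1/20 + 1/80 + 1/40 + 1/60) = 0.32). If labelling drifted after FBT came in, the diagnosis-adjusted and F50.0-only results could be distorted, so the report should interpret the two versions together.

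### No described model contains treatment-start date, so a calendar trend outside the listed covariates would be counted as an FBT effect or would hide one

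*Combined protocol and SAP*

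**What the plan says.** Treatment is fixed by calendar period. Under Participants and recruitment, eligibility covers "all patients initiating treatment during the years 2015-2020" with the eating disorder team. The Background states: "In 2018 the unit implemented FBT, making several changes to the form of family therapy provided". The recruitment section adds: "Patients will be excluded if they were treated during the years 2018-2020 and FBT was never initiated". The comparison cohort is therefore starts in 2015-2017; this is inferred, because the protocol does not put it in words.

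The stated purpose of the main retrospective analysis is to "evaluate whether adoption of FBT has led to faster weight normalisation". The method named for this purpose is "fitting a parametric survival model to the number of days until weight restoration is achieved". Adjusted versions will "fit models with gender, age, baseline weight, comorbid disorders and family structure as covariates". For the secondary endpoints: "Similar parametric survival models will also be used for modelling differences in time to discharge and readmission". No covariates are listed for the Poisson model of adverse events or for the registry analyses. The spline model for weight runs on weeks in treatment, not on calendar date.

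Endpoints and data collection lists the date of treatment start among the items extracted from each record. The only mention of adjusting for when patients began is under Study timeline and plans for dissemination. There it sets each person's registry follow-up date and is not a model term.

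**The concern.** The cohort indicator and calendar time are nearly the same variable, and no patient in either period provides a concurrent comparison. If restoration rates were drifting for other reasons, such as staffing, local practice or referral patterns, the before/after step includes that drift. An upward drift is credited to FBT. A downward drift hides a real benefit. The aim is worded causally, as what adoption has led to, and nothing planned would tell the reader how much of the step could be drift. The data needed to look at this are already being collected.

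**Working it through.** **Plan's own figure.** The Analysis plan reports a type S error of 0.00 and a type M error of 0.89 for 150 patients and a 10% increase in the probability of an event. This could not be reproduced, because the baseline probability, follow-up, cohort split, priors and scale of the 10% are not given. The point does not depend on it, but the scale matters in step 3.

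**Inputs.** Starts 2015-2020 and the switch in 2018 (protocol); 150 patients in the simulation and about 200 expected (protocol). Assumed: even accrual over six years and the switch at the start of 2018.

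1. *Trend that mimics HR 1.10.* Cohort midpoints are mid-2016 and mid-2019, 3 years apart. With yearly growth g in the hazard and no FBT effect, apparent HR = (1+g)^3. Setting this to 1.10 gives g = 1.10^(1/3) - 1 = 3.2% a year. With a midpoint gap of 2.5 or 3.5 years, g is 3.9% or 2.8%. At 5% a year, 1.05^3 = 1.16. A 3% yearly decline gives 0.97^3 = 0.913, which cancels a true HR of 1.10 (1.10 x 0.913 = 1.00).

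2. *If the trend stopped at the end of 2017.* The later cohort then sits only 1.5 years of trend above the earlier midpoint. The required g is 1.10^(1/1.5) - 1 = 6.6% a year, and 3% a year gives only 1.03^1.5 = 1.05.

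3. *Other readings of the 10%.* Control probability p0 is assumed between 0.2 and 0.8, with implied HR = ln(1-p1)/ln(1-p0) and a trend that continues through 2020.

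| Reading | Implied HR | Trend needed per year |
|---|---|---|
| Hazard ratio 1.10 | 1.10 | 3.2% |
| Probability x 1.10 | 1.11-1.32 | 3.6-9.6% |
| Plus 10 percentage points | 1.31-1.60 | 9.5-17% |

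4. *Cost of adding start date.* Code time as uniform on 0 to 6 and the step at 3. The variance of time is 3, the variance of the step is 0.25, and their covariance is 0.5 x 0.5 x (4.5 - 1.5) = 0.75. Then r^2 = 0.75^2/(3 x 0.25) = 0.75 (r = 0.87), and the variance inflation is 1/(1 - 0.75) = 4.0. The standard error doubles.

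5. *Simulation check.* Weibull fits with no FBT effect and a 3.23% yearly trend (assumed baseline rate 1.2 a year, censoring at 2 years). At n = 20,000 the cohort-only model gave HR 1.10, and adding linear start date gave 0.99. The standard error of the log HR rose from 0.18 to 0.37 at n = 150 and from 0.16 to 0.29 at n = 200.

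6. *What the 2015-2017 data can show.* Assume 75-100 patients, all with events. The standard deviation of a uniform start over 3 years is 3/sqrt(12) = 0.866, so the standard error of the yearly log-hazard slope is 1/(0.866 x sqrt(75)) = 0.13, or 1/(0.866 x sqrt(100)) = 0.12. The 3.2% trend is a log slope of ln(1.032) = 0.03. The slope can expose a large drift but cannot rule out a small one.

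**The case against.** The lack of a concurrent control is inherent in a design that the protocol itself calls retrospective and exploratory, and no document shows that outcomes were changing before 2018. The Background says the unit had used family therapy consistently for about 20 years. Both points are fair. They limit the claim to an unexamined possibility, but they do not supply a check, and the causal wording remains.

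Three stronger readings are tempting, and the documents do not support them.

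- *That any improvement already under way in 2015-2017 will be credited to FBT.* This is strictly true only of the unadjusted model. Drift acting through age, gender, baseline weight, comorbidity or family structure is absorbed by the adjusted models, and changes in referral or case detection would act partly through these. Only the remainder is uncontrolled.
- *That about 3% a year is enough to produce the effect the study is planned around.* The plan never states a hazard ratio. HR 1.10 is the least demanding reading, and it also needs the trend to run through 2020. It fits the reported type S of 0.00 poorly: with 150 events, ln(1.10)/sqrt(4/150) = 0.58, a wrong-sign probability of 0.28 (0.061 among significant results). Ten percentage points, with 75 patients per cohort, gives 0.000-0.003 among significant results.
- *That trend checks could decide whether the difference may be attributed to FBT.* At this size they cannot. Splitting 2015-2017 in half puts the midpoints 1.5 years apart. A 3.2% trend then gives HR 1.05 (log 0.05) against a standard error of sqrt(4/100) to sqrt(4/75), or 0.20-0.23, and a two-sided 5% test detects it about 5.5% of the time. Asking only that the date-adjusted step keep its sign is little better: with a standard error of 0.29-0.37, a true HR of 1.10 keeps a positive sign about 60-63% of the time, against 50% with no effect.

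**Conclusion.** The point holds as a limited, cheaply corrected gap. The FBT effect is a before/after step, no described model contains start date, and a trend outside the listed covariates cannot be separated from FBT in either direction. For the registry models, which list no covariates, date is unspecified rather than excluded.

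The size is illustrative only: from about 3% to about 17% a year across readings of the planning effect if the trend runs through 2020, and 6.6% instead of 3.2% for HR 1.10 if it stopped at the end of 2017. These figures assume even accrual, a log-linear trend and, for the probability readings, a control probability of 0.2-0.8. Whether any such trend exists is not known from the documents.

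**What to change.** For time to weight restoration, pre-specify the following before analysis.

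- A sensitivity model with a linear treatment-start-date term plus the 2018 step, reported with its interval beside the main estimate. State the prior on the date slope, because the data separate slope and step poorly and the prior will matter.
- The start-date slope within 2015-2017, reported descriptively with its interval.
- A primary conclusion worded as a change between periods instead of what FBT has led to, with a statement that a secular trend cannot be excluded.

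Do not use either estimate as a pass/fail test for attributing the difference to FBT.

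The cost is one extra model, one slope and a sentence or two of interpretation, with no new data. The date-adjusted standard error roughly doubles, and a linear term through 2020 may absorb gradual FBT uptake, so this stays a sensitivity analysis and the planned model remains the main one.
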